#### 7.2.4 DEVICE ACTIVATION

Device activation will occur two to six weeks after surgery. Prior to fitting the device, the following testing should be completed:

- Unaided audiogram, insert earphones
  - o Pure-tone air conduction thresholds (125 8000 Hz)
  - Pure-tone bone conduction thresholds (500 4000 Hz)

If at least one unaided air conduction threshold between 125 – 1000 Hz is 80 dB or better, investigators should proceed with fitting SONNET EAS/SONNET 2 EAS according to the recommendations in Appendix B, Electric + Acoustic Fitting.

If all unaided air conduction thresholds between 125 – 1000 Hz are poorer than 80 dB, investigators should proceed with fitting SONNET EAS/SONNET 2 EAS according to the recommendations in Appendix B, Electric Only Fitting.

If the subject has also selected a RONDO/RONDO 2/RONDO 3 processor, investigators should program the device according to the recommendations in Appendix B, Electric Only Fitting.

A copy of the programs created for each processor should be sent to the MED-EL Study Monitor at the completion of this interval.

# 7.2.5 FOLLOW-UP INTERVALS

Follow-up testing will occur at 1 month, 3 months, 6 months, and 12 months post-activation. All testing should occur in a sound-treated booth under insert earphones or in the soundfield, with the subject seated one meter from the speaker. Speaker output should be calibrated prior to conducting study-related testing to ensure consistency across clinical trial sites. During soundfield measures, the contralateral ear should be plugged or masked as needed.

All testing should occur with an ear-level processor and be completed prior to making programming changes to the subject's processors. Additionally, processor settings should be verified prior to testing, with testing conducted using the patient's preferred program position and preferred volume and sensitivity settings.

Follow-up intervals will include the outcome measures below, which are also listed in *Table 1*:

Unaided audiogram, insert earphones

- Pure-tone air conduction thresholds (125 8000 Hz)
- o Pure-tone bone conduction thresholds (500 4000 Hz)
- Aided speech testing in quiet, implant ear only, soundfield
  - o CNC Words in quiet at 60 Db SPL
  - o One list of 50 words will be presented to the implant ear at each interval
  - Lists will be randomized at each clinical trial site
  - o Contralateral ear plugged or masked, as needed
- Aided speech testing in noise, implant ear only, soundfield
  - Az Bio Sentences in noise at 60 Db SPL with an SNR of +10 Db
  - Speech and noise will be presented at 0° azimuth
  - Two lists of 20 sentences each will be presented to the implant ear at each interval
  - o Lists will be randomized at each clinical trial site
  - o Contralateral ear plugged or masked, as needed
- Aided speech testing in noise, "everyday listening condition," soundfield
  - o AzBio Sentences in noise at 60 Db SPL with an SNR of +10 Db
  - Speech and noise will be presented at 0° azimuth
  - Two lists of 20 sentences each will be presented in the "everyday listening condition" at each interval
  - Lists will be randomized at each clinical trial site
  - OPTIONAL: testing can also be completed with an SNR of +5 Db
- Subjective questionnaires
  - o APHAB
  - o SSQ

Programming should be completed according to the recommendations in *Appendix B*. A copy of the maps created in each processor should be sent to the MED-EL Study Monitor at the completion of each interval.

# 7.2.6 SCHEDULE OF EVENTS TABLE

		Candidacy/ Pre-op	Surgery	Activation	1 month post- activation	3 months post- activation	6 months post- activation	12 months post- activation
	Informed Consent	Χ						
	Medical Assessment	Х						
	Surgery		Χ					
	Tympanometry	Χ						
	Unaided thresholds	Х		Χ	Χ	Χ	Χ	Χ
Implant Ear	CNC Words 60 Db SPL (Aided)	х			Х	Х	Х	Х
Non-implant Ear		X						
mplant Ear	AzBio 60 Db SPL +10 Db SNR (Aided)	Х			х	х	х	х
Everyday Condition	AzBio 60 Db SPL +10 Db SNR (Aided)	х			х	х	х	х
Everyday Condition	OPTIONAL: AzBio 60 Db SPL +5 Db SNR (Aided)	Х			х	х	х	х
	APHAB	Χ			Χ	Χ	Χ	Χ
	SSQ	Χ			Χ	Χ	Χ	Χ

(TABLE 1)

# 7.3 PRECAUTIONARY PROCEDURES

The MED-EL SYNCHRONY/SYNCHRONY PIN and SYNCHRONY 2/SYNCHRONY 2 PIN Cochlear Implant is MR conditional. Subjects in the study may undergo an MRI at 1.5 or 3.0 Tesla, if required, over the duration of the study. Additional details on MRI scanning procedures can be found in the Medical Procedures Manual, available at: http://www.medel.com/us/isi-cochlear-implant-systems/.

#### 7.4 PROHIBITED PROCEDURES

Subjects may not receive an additional hearing implant on the contralateral ear during the course of the study.

In cases where residual hearing should be preserved, the Insertion Electrode is also contraindicated as a tool for assessing insertion depth.

# **8** ASSESSMENT OF SAFETY

### 8.1 DEFINITIONS AND CLASSIFICATIONS

As noted in Section 4.2, device-related adverse events will be recorded throughout the duration of the study to satisfy the safety endpoint. Adverse device effects will be reported as the number and proportion of subjects experiencing device or procedure-related adverse events. Reportable events and procedures are described below in Sections 8.1.1 through 8.1.3, 8.2, and 8.3.

# 8.1.1 DEFINITION OF ADVERSE EVENTS (AE)

An adverse event is any unfavorable change in the health of a participant, including abnormal test results, that happens during a clinical study or immediately after the study has ended. This change may or may not be caused by the intervention studied.

### 8.1.2 DEFINITION OF ADVERSE DEVICE EFFECTS (ADE)

Adverse events will be reported as related to the device if the event is known to occur with cochlear implant use or if there is a reasonable possibility that the cochlear implant caused the event. Reasonable possibility means that there is evidence to suggest a causal relationship between the device and the event. Events occurring immediately after implantation or use of the device may also suggest a device-related adverse event.

Events can also be noted as procedure-related complications. Procedure-related events are those that do not directly result from use of the device. Examples of procedure-related complications include anesthetic-related complications associated with cochlear implantation.

# 8.1.3 DEFINITION OF SERIOUS ADVERSE EVENTS (SAE)

Adverse events are considered serious when they result in death or any injury or illness that is life-threatening, results in permanent impairment or damage to the body, or requires medical or

Page 20 of 35

https://clinicaltrials.gov/ct2/about-studies/glossary

surgical intervention to prevent permanent harm to the body. Serious adverse events will only be reported if they are deemed related to the device or procedure.

Examples of serious adverse events that would be reportable include infection or device failure requiring explantation of the cochlear implant.

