#### 8.3 REPORTING PROCEDURES

# 8.3.1 ADVERSE EVENT REPORTING

Any adverse device effect discovered in the course of the study should be reported on the Adverse Event CRF by an investigator according to Section 8.1 and reported to MED-EL. Investigators are responsible for determining whether or not the adverse event meets the definitions for device-related, serious, and/or unanticipated. Questions regarding classification should be brought to the attention of the MED-EL Clinical Monitor. All Aes should be reported to

the MED-EL Clinical Monitor in a timely manner. All adverse events deemed related to the device or procedure will be reported to the FDA and to relevant IRBs in the annual report.

Investigators should reference the below flow chart (*Figure 2*) as well as Section 8.3.2 to determine appropriate reporting procedures, depending on AE type.

(FIGURE 2)

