#### 8.4 STUDY HALTING RULES

Adverse events will be reviewed by MED-EL throughout the duration of the study. Review of serious, unexpected, and device related adverse events by MED-EL will determine whether the study should continue per the protocol, be modified, or be discontinued.

Examples of findings that would trigger a safety review are the number of serious adverse events occurring overall, the number of occurrences of a particular type of serious adverse event, or increased frequency of events (e.g. device deficiencies). If findings indicate the study or protocol should be reconsidered, MED-EL will inform FDA of the disposition of the study.

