# 10.4.3 ANALYSIS OF THE SECONDARY ENDPOINT(S)

Secondary endpoints will not be formally tested but will be summarized using appropriate descriptive statistics. Details of the methods used will be laid out in the SAP.

The number and percentage of subjects performing similarly or better on AzBio at 6 months postoperatively compared to the pre-operative aided condition will be summarized. Responses from the APHAB and SSQ questionnaires will also be summarized descriptively. The number and percentage of subjects with complete hearing preservation, partial hearing preservation, minimal hearing preservation, and loss of hearing (according to the HEARRING classification) will also be summarized. Adverse events will be summarized by the number and percent of subjects experiencing adverse events.

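### Sections 8.1.3, 8.2, 8.3.1 and 8.4 disagree on which serious adverse events reach the sponsor; if 8.1.3 is applied, an overall count cannot be formed

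*Combined protocol and SAP*

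**What the plan says.** - **Section 8.1.3** defines serious events, counting death among them, and then restricts reporting: "Serious adverse events will only be reported if they are deemed related to the device or procedure". It names no recipient and makes no exception.
- **Section 8.3.1** leaves the classification to the site: "Investigators are responsible for determining whether or not the adverse event meets the definitions for device-related, serious, and/or unanticipated". It also contains an unrestricted instruction, "All Aes should be reported to" the sponsor's clinical monitor, followed by a restricted one: "All adverse events deemed related to the device or procedure will be reported to the FDA and to relevant IRBs in the annual report".
- **Section 8.2** requires adverse device effects on the adverse event CRF and tells investigators to record reportable events that start after consent. The form collects seriousness and relationship to the device.
- **Section 8.4** describes the sponsor's review in two ways: "Review of serious, unexpected, and device related adverse events by MED-EL will determine whether the study should continue per the protocol", and "Examples of findings that would trigger a safety review are the number of serious adverse events occurring overall". It gives no numerical threshold.
- **Section 10.4.3** says: "Adverse events will be summarized by the number and percent of subjects experiencing adverse events". No relatedness limit appears in that sentence.

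**The concern.** Under 8.1.3, relatedness decides whether a serious event is reported at all; it is not simply recorded about each event. A site that follows 8.1.3 would withhold a serious event it judged unrelated, while a site that follows the all-events sentence in 8.3.1 would send it. With six sites (Protocol Summary and section 5.3), collection could differ from site to site.

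At stake is the sponsor's oversight. This is a one-arm trial (section 10.7), so no concurrent control rate exists and the safety review rests on a complete count. Section 8.1.4 treats an unexpected degree of incidence as a ground for calling an effect unanticipated, and incidence is hard to judge when some events were removed beforehand. Section 2.2.1 adds that these subjects may have more residual hearing to lose than traditional candidates, so attribution matters here.

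**Working it through.** The plan gives no figure to reproduce on this point, so the check sets the passages side by side.

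**Step 1: what counts as reportable.** Section 8.2 limits recording to reportable events. Section 8.1 says these are described in 8.1.1 to 8.1.3, 8.2 and 8.3, which are the sections that disagree. Section 8.1.3 uses the same word when it gives its examples of serious events. A site reading 8.1.3 and 8.2 together could therefore conclude that an unrelated serious event need not be recorded.

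**Step 2: trace one serious event judged unrelated.**

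| Section | Treatment of the event |
|---|---|
| 8.1.3 | Not reported |
| 8.2 | Not an adverse device effect, so no CRF is expressly required |
| 8.3.1, all-events sentence | Goes to the clinical monitor |
| 8.3.1, annual report sentence | Does not go to FDA or IRBs |
| 8.4, example trigger | Counted, if overall means every serious event |
| 8.4, description of the review | Outside it, if the three adjectives form one joint condition |

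**Step 3: trace one serious event judged related.** Every rule lets it reach the sponsor. The inconsistency therefore concerns only events judged unrelated.

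**Step 4: the effect on the count.** Let R be the number of serious events judged related and U the number judged unrelated.

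- Overall count = R + U.
- If 8.1.3 governs, the sponsor receives R and the shortfall is (R + U) − R = U.
- If the all-events sentence governs, the sponsor receives R + U and the shortfall is 0.

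The documents give no expected value for R or U and no rate at which related events are misjudged as unrelated. The shortfall U therefore cannot be estimated. One subject out of 50 is 1/50 = 2 percentage points, but that is only the scale of a subject-level proportion and does not measure the defect.

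**The case against.** The strongest reply is that the text describes two channels. Section 8.1.3 names no recipient, and 8.3.1 places all events to the monitor next to related events to FDA and IRBs. If 8.1.3 concerns only the second channel, every sentence can be followed. The seriousness and device-relationship fields on the CRF give this some support, since a relationship field has less use if only related events are entered. Figure 2 is not shown and may settle the routing. This reading is possible, so it would be too strong to say that the passages cannot all be followed. But the visible text does not state it, and the 8.2 wording leans the other way.

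A reader might also infer that the safety review has no input. The documents do not support that. Related serious events reach it under any reading, and all events do if the 8.3.1 sentence governs. In 8.4 the word overall is set against a particular type of event, so it may mean across types, and the triggers are only examples.

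A reader might count section 10.4.3 as a further conflict. It can be shorthand for the endpoint that the Protocol Summary and sections 4.2.2 and 8.1 limit to related events, so it adds little.

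There are partial safeguards. Section 8.1.2 sets a broad test of relatedness, 8.3.1 sends classification questions to the monitor, and sections 11 and 12 provide access to source and sampled checks. Those checks compare a sample of CRFs with source, so an event with no form is not among the items sampled, although a monitor might still notice it.

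Finally, a reader might try to size the bias by supposing that some related events are misjudged as unrelated. Any such rate would be invented. The endpoint counts subjects, so a second event in the same subject would not move it.

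**Conclusion.** The inconsistency is real and should be resolved. The visible text of 8.1.3, 8.2, 8.3.1 and 8.4 does not establish which serious events reach the sponsor. The consequence is conditional: if the 8.1.3 restriction is applied as written, serious events judged unrelated by the investigator are not reported to the sponsor, an overall count cannot be formed, and relatedness cannot be routinely re-reviewed. The loss is confined to those events, and its size cannot be estimated from the documents. The conclusion assumes that Figure 2 does not already settle the routing; even if it does, the sentences in 8.1.3 and 8.3.1 would need to be aligned with it. The primary effectiveness analysis is not affected.

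**What to change.** Reconcile the four sections, and Figure 2, as follows:

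- Record every serious adverse event after consent on the existing adverse event CRF and send it to the sponsor's monitor.
- Record device relatedness (already a field) and procedure relatedness (not among the fields listed in 8.2) as attributes of each event.
- State that the relatedness restriction in 8.1.3 applies only to FDA and IRB reporting.
- Use the full list of serious events for the 8.4 review.
- Tabulate the number of subjects with serious events twice: overall, and related only.

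Leave the related-event safety endpoint and the reporting in 8.3.2 unchanged. The change makes re-review of relatedness possible but does not by itself correct a misjudged event; someone must still reclassify it. The cost is a few more forms per site and a short protocol edit, with no new visits.

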#### 8.1.4 DEFINITION OF UNANTICIPATED ADVERSE DEVICE EFFECTS (UADE)

Unanticipated adverse device effects are defined as any event not previously in the investigational plan or IC. Risks associated with the device and procedure are detailed in Section 2.2.1 above. Events can be unexpected in nature, severity, or degree of incidence. This definition could include an unanticipated adverse device effect or other serious adverse effect associated with the device, if the problem was not previously identified in nature, severity, or degree of incidence.

#### 8.2 TIME PERIOD AND FREQUENCY FOR EVENT ASSESSMENT AND FOLLOW-UP

The occurrence of an adverse event may be brought to the attention of the investigator during study visits, interim visits, or phone conferences over the duration of the study. All adverse device effects will be reported on the Adverse Event Report Form CRF. Information to be collected on the Adverse Event Report Form CRF includes: event description, date of onset, time of onset, seriousness, relationship to the device, unexpectedness, and the date/time of resolution (if applicable). Adverse events will continue to be followed until reaching adequate resolution or stabilization.

Investigators should record all reportable events with start dates occurring any time after the IC is obtained. Any medical condition that is present at the enrollment/baseline evaluation will not be reported as an adverse event. If the subject's condition deteriorates at any time during the study, however, the event will be reported.

Adverse events recorded as intermittent or fluctuating require documentation of onset and duration of each episode. This will be in addition to the original onset date of the event. Aes should not be recorded as resolved unless the reported event is no longer present and is not expected to reoccur.

[figure not shown]
#### 8.3 REPORTING PROCEDURES

# 8.3.1 ADVERSE EVENT REPORTING

Any adverse device effect discovered in the course of the study should be reported on the Adverse Event CRF by an investigator according to Section 8.1 and reported to MED-EL. Investigators are responsible for determining whether or not the adverse event meets the definitions for device-related, serious, and/or unanticipated. Questions regarding classification should be brought to the attention of the MED-EL Clinical Monitor. All Aes should be reported to

the MED-EL Clinical Monitor in a timely manner. All adverse events deemed related to the device or procedure will be reported to the FDA and to relevant IRBs in the annual report.

Investigators should reference the below flow chart (*Figure 2*) as well as Section 8.3.2 to determine appropriate reporting procedures, depending on AE type.

(FIGURE 2)

# 8.3.2 UNANTICIPATED SERIOUS ADVERSE DEVICE EFFECT REPORTING

If the investigator determines that the adverse device effect is unanticipated and serious, the CRF should be submitted to the MED-EL Study Monitor no later than 10 working days after becoming aware of the event. Additionally, the investigator should notify the reviewing IRB of the unanticipated serious adverse device effect within 10 working days.

Upon receiving this documentation, MED-EL will review the information contained in the CRF. After completing this review, MED-EL will submit the information to FDA, as well as all principal investigators for submission to reviewing IRBs within 10 working days. Additional reports concerning the effect will be submitted upon FDA request.

#### 8.4 STUDY HALTING RULES

Adverse events will be reviewed by MED-EL throughout the duration of the study. Review of serious, unexpected, and device related adverse events by MED-EL will determine whether the study should continue per the protocol, be modified, or be discontinued.

Examples of findings that would trigger a safety review are the number of serious adverse events occurring overall, the number of occurrences of a particular type of serious adverse event, or increased frequency of events (e.g. device deficiencies). If findings indicate the study or protocol should be reconsidered, MED-EL will inform FDA of the disposition of the study.

#### 9 CLINICAL MONITORING

Clinical site monitoring is conducted to ensure that the rights and well-being of subjects are protected, that the reported trial data are accurate, complete, and verifiable from source documents, and that the trial is being conducted in compliance with the currently approved protocol/amendment(s), with GCP, and with applicable regulatory requirements. MED-EL Corporation personnel and/or a qualified Contract Research Organization (CRO) will be responsible for monitoring this investigation according to MED-EL Corporation's SOPs.

Clinical monitors will conduct on-site pre-investigation site visits at each prospective site. During this visit, the monitor will evaluate the facilities and staff and review study-specific details and obligations with the investigators. Investigators will demonstrate understanding of the following information at the conclusion of the pre-investigation site visit:

- Obligation to conduct the study in accordance with the investigator agreement, GCP, and other applicable regulations
- Device accountability and traceability requirements for investigational devices
- Requirements for a well-controlled study
- Investigator's role in the process of obtaining IC
- Obligation to obtain and maintain IRB approval

- Importance of complete and accurate study records, including source documentation
- Required monitoring and clinical monitor access to the study records
- Time commitments for investigators involved in the study
- Details specific to the investigational plan

Once the study has been initiated and enrollment has begun, periodic on-site monitoring visits will occur. The frequency of these visits will depend on the number of subjects enrolled, the completion or accuracy of study records received by MED-EL, and the occurrence of adverse events and protocol deviations. These periodic on-site visits will evaluate whether:

- The facilities continue to be acceptable for the study
- The investigational plan is being followed
- Changes to the investigational plan have been reported to and approved by the IRB
- Records are accurate, complete, and current
- Reports to the Sponsor and IRB are accurate, complete, and on time

After completion of any monitoring visit, the clinical monitor will document the observation, conclusions, and corrective actions taken to address any findings. The documentation will include the visit date, name of the monitor, name of the investigator and site, and address of the site.

Case report forms and other related study documentation will be reviewed as MED-EL receives the completed paperwork throughout the duration of the study. Completed study records will be reviewed 100% for missing data entries. Accuracy of study records will be monitored based on the investigator's history, accuracy of study records, the rate of adverse events, and the occurrence of protocol deviations.

